In both Part 1 and Part 2 participants will have a screening visit within 30 days prior to first dose, a minimum 10-day washout period between doses (Part 1 only), and a follow-up visit 7 to 14 days after the last dose. The maximum duration of study participation will be approximately 9 to 10 weeks for Part 1 and 8 to 9 weeks for Part 2.

Study Schematic

[figure not shown]
Part 1

Treatments A and B will be Capsule and Tablet administered in a randomized crossover design with 100 mg Ritonavir with food (fed state) (Part 1A).

Treatment C will be Tablet assessed in Part 1A, administered with 100 mg Ritonavir without food (fasted state) (Part 1B)

Part 2

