6.1. Inclusion Criteria

A participant will be eligible for inclusion in this study only if all of the following criteria apply:

AGE

1. Between 18 and 55 years of age inclusive, at the time of signing the informed consent.

TYPE OF PARTICIPANT AND DIAGNOSIS INCLUDING DISEASE SEVERITY

- 2. Healthy as determined by the Investigator or medically qualified designee based on a medical evaluation including medical history, physical examination, laboratory tests and cardiac monitoring.
- 3. A participant with a clinical abnormality or laboratory parameter(s) which is/are not specifically listed in the inclusion or exclusion criteria, and outside the reference range for the population being studied, may be included only if the Investigator in consultation with the Medical Monitor, if required, agree and document that the finding is unlikely to introduce additional risk factors and will not interfere with the study procedures.
- 4. A creatinine clearance > 80 mL/min as determined by Cockcroft-Gault equation: CLcr (mL/min) = (140 age) * Wt / (72 * Scr) (times 0.85 if female) where age is in years, weight (Wt) is in kg, and serum creatinine (Scr) is in units of mg/dL.

WEIGHT

5. Body weight \geq 50.0 kg (110 lbs.) for men and \geq 45.0 kg (99 lbs) for women and body mass index (BMI) within the range 18.5 to 31.0 kg/m² (inclusive).

SEX

6. Males or females

A female participant is eligible to participate if she is not pregnant (as confirmed by a negative serum human chorionic gonadotrophin [hCG] test), not lactating, and of non-reproductive potential which is defined as:

Reproductive potential:

There is no definitive drug-drug interaction (DDI) information with GSK2838232 and an interaction with oral contraceptives is possible, so other (barrier,

inter-uterine device etc.) methods of contraception will be required.

Females of reproductive potential may only be enrolled if they are using two forms of complementary contraception, which must include at least one barrier method. They will be counselled on safer sex practices.

Fertile females, who have an established, long-term lifestyle of sexual abstinence, or only same sex partners, require no other means of birth control.

Non-reproductive potential:

- Pre-menopausal females with one of the following:
 - Documented tubal ligation,
 - Documented hysteroscopic tubal occlusion procedure with follow-up confirmation of bilateral tubal occlusion,
 - Hysterectomy,
 - Documented Bilateral Oophorectomy.

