- Postmenopausal defined as 12 months of spontaneous amenorrhea in questionable cases a blood sample with simultaneous follicle stimulating hormone (FSH) and estradiol levels consistent with menopause (refer to laboratory reference ranges for confirmatory levels). Females on hormone replacement therapy (HRT) must discontinue HRT to allow confirmation of post-menopausal status prior to study enrolment.

Male participants with female partners of child bearing potential must comply with the following contraception requirements from the time of first dose of study medication until one week after the last dose of study medication.

- a. Vasectomy with documentation of azoospermia.
- b. Male condom plus partner use of one of the contraceptive options below:
 - Contraceptive subdermal implant that meets the Standard operating Procedure (SOP) effectiveness criteria including a <1% rate of failure per year, as stated in the product label,
 - Intrauterine device or intrauterine system that meets the SOP effectiveness criteria including a <1% rate of failure per year, as stated in the product label,
 - Oral contraceptive, either combined or progestogen alone or Injectable progestogen,
 - Contraceptive vaginal ring,
 - Percutaneous contraceptive patches.

These allowed methods of contraception are only effective when used

consistently, correctly and in accordance with the product label. The Investigator is responsible for ensuring that participants understand how to properly use these methods of contraception.

INFORMED CONSENT

7. Capable of giving signed informed consent, which includes compliance with the requirements and restrictions listed in the consent form and in this protocol.

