9.2.5. Pregnancy

- Details of all pregnancies in female participants and female partners of male participants will be collected after the start of study treatment and until the final follow-up visit.
- If a pregnancy is reported, the Investigator should inform GSK within 24 hours of learning of the pregnancy and should follow the procedures outlined in Section 12.6, Appendix 6.
- Abnormal pregnancy outcomes (e.g., spontaneous abortion, fetal death, stillbirth, congenital anomalies, ectopic pregnancy) are considered SAE.

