12.6. Appendix 6: Contraceptive Guidance and Collection of Pregnancy Information

Definitions

Woman of Childbearing Potential (WOCBP)

A woman is considered fertile following menarche and until becoming post-menopausal unless permanently sterile (see below).

Women in the following categories are not considered WOCBP

- 7 Premenarchal
- 8. Premenopausal female with ONE of the following:
- Documented hysterectomy
- Documented bilateral salpingectomy
- Documented bilateral oophorectomy

Note: Documentation can come from the site personnel's: review of participant's medical records, medical examination, or medical history interview.

- 9. Postmenopausal female
- A postmenopausal state is defined as no menses for 12 months without an alternative medical cause. A high follicle stimulating hormone (FSH) level in the postmenopausal range may be used to confirm a postmenopausal state in women not using hormonal contraception or hormonal replacement therapy (HRT). However, in the absence of 12 months of amenorrhea, a single FSH measurement is insufficient.
- Females on HRT and whose menopausal status is in doubt will be required to use one of the non-hormonal highly effective contraception methods if they wish to continue their HRT during the study. Otherwise, they must discontinue HRT to allow confirmation of postmenopausal status before study enrollment.

Contraception Guidance

Male participants

- Male participants with female partners of child-bearing potential are eligible to participate if they agree to ONE of the following (during the protocol-defined time frame in Section 6.1):
 - Are abstinent from penile-vaginal intercourse as their usual and preferred lifestyle (abstinent on a long term and persistent basis) and agree to remain abstinent.
 - Agree to use a male condom plus an additional method of contraception with a failure rate of < 1% per year when having penile-vaginal intercourse with a woman of childbearing potential as described in Table 6.

- Men with a pregnant or breastfeeding partner must agree to remain abstinent from penile-vaginal intercourse or use a male condom during each episode of penile penetration (during the protocol-defined time frame).
- Refrain from donating sperm for duration of study and for 3 months after study completion or from last dose.

Female participants

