Female participants of childbearing potential are eligible to participate if they agree to use a highly effective method of contraception consistently and correctly as described in Table 6.

Table 6 Highly Effective Contraceptive Methods

Highly Effective Contraceptive Methods That Are User Dependent ^a

Failure rate of <1% per year when used consistently and correctly.

Combined (estrogen- and progestogen-containing) hormonal contraception associated with inhibition of ovulation^b

- oral
- intravaginal
- transdermal

Progestogen-only hormonal contraception associated with inhibition of ovulation^b

injectable

Highly Effective Methods That Are User Independent

- Implantable progestogen-only hormonal contraception associated with inhibition of ovulation^b
- Intrauterine device (IUD)
- Intrauterine hormone-releasing system (IUS)
- bilateral tubal occlusion

Vasectomized partner

(A vasectomized partner is a highly effective contraception method provided that the partner is the sole male sexual partner of the WOCBP and the absence of sperm has been confirmed. If not, an additional highly effective method of contraception should be used.)

Sexual abstinence

(Sexual abstinence is considered a highly effective method only if defined as refraining from heterosexual intercourse during the entire period of risk associated with the study drug. The reliability of sexual abstinence needs to be evaluated in relation to the duration of the study and the preferred and usual lifestyle of the participant).

NOTES:

- a. Typical use failure rates may differ from those when used consistently and correctly. Use should be consistent with local regulations regarding the use of contraceptive methods for participants in clinical studies.
- b. Hormonal contraception may be susceptible to interaction with the study drug, which may reduce the efficacy of the contraceptive method. In this case two highly effective methods of contraception should be utilized during the treatment period and for at least 30 days, 5 half-lives or twice the duration of the biological effect of the investigational product (whichever is longer) after the last dose of study treatment

Pregnancy Testing

- WOCBP should only be included after a confirmed menstrual period and a negative highly sensitive urine or serum pregnancy test

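### Pregnancy collection ends at the follow-up visit 7 to 14 days after the last dose, before the 30-day post-dose contraception period that Appendix 6 sets for some women, and late-recognised pregnancies have no explicit route

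*Protocol*

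**What the plan says.** Protocol Section 9.2.5 sets the collection window: pregnancies in female participants and "female partners of male participants will be collected after the start of study treatment and until the final follow-up visit". The Synopsis places that visit: "a follow-up visit 7 to 14 days after the last dose". Appendix 6 (Section 12.6) limits collection to pregnancies that arise during study participation, and under Section 5.3 the follow-up visit is the last phase a participant completes.

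The protocol states three post-dose precautions:

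- **Women, conditional.** Table 6 note b in Appendix 6 warns: "Hormonal contraception may be susceptible to interaction with the study drug, which may reduce the efficacy of the contraceptive method". Where this applies, the note says that "two highly effective methods of contraception should be utilized during the treatment period and for at least 30 days, 5 half-lives". It adds a third alternative, double the length of time the drug has a biological effect, and the longest of the three applies. Section 6.1 says "an interaction with oral contraceptives is possible" but gives no post-dose duration for women.
- **Men, contraception.** Under Section 6.1, men with partners of child-bearing potential must follow "contraception requirements from the time of first dose of study medication until one week after the last dose of study medication".
- **Men, sperm donation.** Appendix 6: "Refrain from donating sperm for duration of study and for 3 months after study completion or from last dose".

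After the study, Section 9.2.1 and the end of Appendix 6 require reporting of an SAE judged reasonably related to study treatment if the investigator learns of it. Neither requires active seeking.

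**The concern.** The protocol treats pregnancy as a safety outcome. The sponsor is to be told within 24 hours of the investigator learning of it, and the pregnancy is followed to its outcome, up to 6 to 8 weeks past the estimated delivery date. Collection nevertheless stops at a visit that precedes the end of a precaution the same protocol imposes. If the 30-day period in note b reflects a time when conception under exposure matters, most of it lies outside the period in which anyone is required to record a pregnancy.

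A second gap does not depend on which window is right. Section 9.2.5 ties collection to calendar time and does not say whether the date of conception or the date of recognition counts. A pregnancy conceived during dosing, or in the days before follow-up, may not be apparent at the visit. The schedules (Tables 2 and 3) plan a follow-up pregnancy test for women participants only, so a partner's pregnancy must be noticed and reported by then.

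The stake is completeness of safety data in a small healthy-volunteer study. No PK endpoint, interval estimate or sample size is involved.

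**Working it through.** The plan gives no figure of its own on this point. The check is date arithmetic and a comparison of passages.

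**Inputs**

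- Follow-up visit, F: day 7 to day 14 after the last dose (Synopsis; Section 5.1).
- Conditional window for women, W: at least 30 days (Appendix 6, Table 6 note b).
- Male contraception window: 7 days (Section 6.1).
- Half-life: 15 to 18 h alone and 34 to 42 h with steady-state RTV (Section 3.2.1).

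**Days after collection ends** = max(0, W − F)

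| Precaution | F = 7 | F = 14 |
|---|---|---|
| Women, note b (30 days) | 30 − 7 = 23 days, 23/30 = 76.7% | 30 − 14 = 16 days, 16/30 = 53.3% |
| Male contraception (7 days) | 7 − 7 = 0 days | 7 − 14 < 0, so 0 days |

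**Does 30 days govern in note b?** Note b takes the longest of three periods. Five half-lives = 5 × t½ / 24:

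- Without RTV: 5 × 15 / 24 = 3.1 days to 5 × 18 / 24 = 3.8 days.
- With steady-state RTV: 5 × 34 / 24 = 7.1 days to 5 × 42 / 24 = 8.8 days.

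Both are shorter than 30 days. The duration of biological effect is not given, so 30 days is a lower bound and 16 to 23 days is the smallest gap note b allows.

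**Late recognition, passages side by side**

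- Section 9.2.5: collection runs until the final follow-up visit. It does not mention a pregnancy conceived before that visit and recognised after it.
- Appendix 6: collection applies to someone who becomes pregnant during participation. This can be read as covering such a case, but the text does not say so.
- Section 9.2.1 and the end of Appendix 6: after the study, only related SAEs that come to the investigator's attention.

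An uncomplicated pregnancy conceived after follow-up, or one whose SAE is judged unrelated, therefore has no stated route. One conceived before follow-up but recognised later has a route only on a favourable reading of Appendix 6.

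**The case against.** The strongest reply is that the mismatch is narrow. Note b is not a rule for all women: it applies where hormonal contraception may interact. Section 6.1 already requires two complementary forms including a barrier method, and asks for non-hormonal methods because of the possible interaction. The affected subset may be small or empty. This stands, and the 16 to 23 days should be claimed only for those women. The condition is still live, since Table 6 lists hormonal methods as acceptable.

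For men, the contraception rule ends one week after the last dose and follow-up covers it fully. This also stands. A reader might set the three-month sperm-donation bar against the collection window and infer that most of the male risk period is missed. With three months taken as 90 days, 76 to 83 days would lie beyond follow-up. The documents do not support that reading: Section 9.2.5 concerns partners of participants, and donation is a separate restriction.

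Late recognition is partly handled. Appendix 6 starts its 24-hour clock when the investigator learns of the pregnancy, allows testing after the last dose, and calls for a test when a menstrual cycle is missed. That supports the favourable reading but leaves Section 9.2.5 silent.

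A reader might also infer that a Day 7 visit fails to cover even five half-lives. At most this concerns boosted Part 1, with a shortfall of 0.1 to 1.8 days. It assumes that the half-life seen with RTV 100 mg daily for 10 days applies after two RTV pre-doses plus one dose given with GSK2838232. In unboosted Part 2, five half-lives end well before follow-up. The point does not rest on this.

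**Conclusion.** The concern holds in limited form. Collection under Section 9.2.5 ends 16 to 23 days (53 to 77%) short of the minimum 30-day period in note b, for women on hormonal contraception that may interact with the study drug. A pregnancy in a participant or partner that is conceived before follow-up and recognised later has no explicit route in Section 9.2.5. The one-week and three-month male periods are not aligned with each other.

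It would be too strong to say that such pregnancies are never captured. Related SAEs from post-study pregnancies are reportable if the investigator learns of them; Section 9.2.5 counts abnormal outcomes as SAEs, and Appendix 6 always counts spontaneous abortion as one. What is missing is required collection.

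The size rests on the stated 7-to-14-day visit and on 30 days being the governing limb of note b; a longer biological effect would widen the gap. The number of women affected is not given and could be zero. This is a cheap improvement to safety capture.

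**What to change.** Reconcile Section 6.1, Section 9.2.5 and Appendix 6 (the male contraception and sperm-donation periods, Table 6 note b, and the pregnancy-collection paragraphs). No position is taken on which clinical window is right; that is for the sponsor to settle and state once.

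Then, for data collection only:

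- Define the pregnancies to be collected by estimated date of conception, from first dose to the end of whichever post-dose contraception window the sponsor retains, whenever they are recognised. Use the same definition in Appendix 6.
- Instruct participants at the follow-up visit to report any such pregnancy, their own or a partner's.
- Optionally, make one telephone contact when that window closes with participants of child-bearing potential or with such partners.

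The cost is protocol and consent wording, a few contacts among the roughly 26 participants planned (16 in Part 1 and 10 in Part 2), and somewhat later closure of pregnancy reports. The PK analyses and the sample size do not change.

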9.2.6. Total Blood Volume

No more than 500 mL of blood will be collected over the duration of the study, from an individual participant, including any extra assessments that may be required.

9.3. Treatment of Overdose

For this study, any dose of GSK2838232 greater than the planned dose for any given participant in each treatment period within a 24-hour time period (\pm 1 hour) will be considered an overdose.

For this study any dose of RTV greater than the planned dose (100 mg once daily) within a 24-hour time period (\pm 1 hour) will be considered an overdose.

In the event of an overdose the Investigator or treating physician should:

- Contact the GSK Medical Monitor immediately.
- Closely monitor the participant for AEs/SAEs and laboratory abnormalities until GSK2838232 can no longer be detected systemically (at least 7 days for GSK2838232).
- Obtain a plasma sample for PK analysis within 5 days from the date of the last dose of study treatment if requested by the Medical Monitor (determined on a case-by-case basis).
- Document the quantity of the excess dose as well as the duration of the overdosing in the CRF.

Decisions regarding dose interruptions or modifications will be made by the Investigator in consultation with the Medical Monitor based on the clinical evaluation of the participant.

9.4. Safety Assessments

Planned time points for all safety assessments are provided in the Schedule of Assessments (Table 2 and Table 3).

9.4.1. Physical Examinations

• A complete physical examination will include, at a minimum, assessment of the Cardiovascular, Respiratory, Gastrointestinal and Neurological systems. Height and weight will also be measured and recorded.

CONFIDENTIAL

- A brief physical examination will include, at a minimum assessments of the lungs, cardiovascular system and abdomen (liver and spleen).
- Investigators should pay special attention to clinical signs related to previous serious illnesses.

9.4.2. Vital Signs

- Vital signs will be measured in supine position after 10 minutes rest and will include systolic and diastolic blood pressure (BP) and heart rate (HR);
- BP and HR to be taken in triplicate (taken 5 minutes apart) at pre-dose (Part 1: Day 1; Part 2: Day 1 and Day 11) and singular at all other measurement time points;
- If a blood pressure is outside the normal limits (< 90 mmHg or > 160 mmHg), then additional measurements should be taken each minute for 2 more occasions.
- If a HR is outside the normal limits (< 40 bpm or > 100 bpm) then additional measurements should be taken 5 minutes apart for 2 more occasions.
- Ensure correct sized cuff is used for arm circumference.
- It is acceptable that HR be captured from continuous ECG equipment, 12-lead ECG or BP equipment.
- The GSK Medical Monitor should be notified for any clinically significant changes in vital signs.

9.4.3. Electrocardiograms

- Triplicate 12-lead ECGs will be obtained at least 5 minutes apart in the supine position after 10 minutes of rest pre-dose (Part 1: Day 1; Part 2: Day 1 and Day 11). All values will be recorded.
- Singular 12-lead ECGs will be recorded at all other timepoints using an ECG machine that automatically calculates the HR and measures PR, QRS, QT and QTcF intervals.

- Refer to Section 8.1.2 for QTc withdrawal criteria and additional QTc readings that may be necessary.
- The Investigator will review the 12-lead ECGs. The decision to run repeat measurements if a result is outside of the normal predicted range (and/or considered clinically significant) should be made by the PI based on their clinical judgement to ensure participant safety.

9.4.4. Holter Monitoring

Cardiac monitoring (24 hour) will be performed using Holter monitoring during the screening process as shown in the Schedule of Assessments (Table 2 and Table 3). Holter monitoring may take place during the study period if needed.

Start date and time, stop date and time, interpretation, and nature of abnormality, if any, will be captured in the study database. Analysis of the Holter monitoring will consider the following:

- HR (brady and tachycardia).
- Normal and aberrant beats.
- Number of supraventricular contractions, premature atrial contractions, supraventricular tachycardias, premature ventricular contractions, couplets, triplets and ventricular tachycardias.
- Atrio-ventricular conduction defects.
- Atrial fibrillation and flutter.

9.4.5. Clinical Safety Laboratory Assessments

- Refer to Section 12.2, Appendix 2 for the list of clinical laboratory tests to be performed and to the Schedule of Assessments (Table 2 and Table 3) for the timing and frequency.
- The Investigator must review the laboratory report, document this review, and record any clinically relevant changes occurring during the study in the AE section of the CRF. The laboratory reports must be filed with the source documents. Clinically significant abnormal laboratory findings are those which are not associated with the underlying disease, unless judged by the Investigator to be more severe than expected for the participant's condition.
- All laboratory tests with values considered clinically significantly abnormal during participation in the study or within 7 days after the last dose of study treatment should be repeated until the values return to normal or baseline or are no longer considered significantly abnormal by the Investigator or medical monitor.
- If such values do not return to normal/baseline within a period of time judged reasonable by the Investigator, the etiology should be identified and the sponsor notified.

• All protocol-required laboratory assessments, as defined in Section 12.2, Appendix 2, must be conducted in accordance with the laboratory manual and the Schedule of Assessments (Table 2 and Table 3).

205820

• If laboratory values from non-protocol specified laboratory assessments performed at the institution's local laboratory require a change in participant management or are considered clinically significant by the Investigator (e.g., SAE or AE or dose modification), then the results must be recorded in the CRF.

